13. ADVERSE EVENTS

13.1. Definitions and Classifications

Adverse Event (AE) – An AE is “any untoward medical occurrence, unintended disease or injury, or untoward clinical signs (including abnormal laboratory findings) in subjects, users or other persons, whether or not related to the investigational medical device.”

Note: This definition includes events related to the investigational medical device or the comparator, and to the procedures involved. For users or other persons, this definition is restricted to events related to investigational medical devices.¹

An AE includes any condition (including a pre-existing condition) that:

1. Was not present prior to the study, but appeared or reappeared following initiation of the study.

Clinical Study Protocol

Johnson & Johnson Vision Care, Inc.

2. Was present prior to the study but worsened during the study. This would include any condition resulting from concomitant illnesses, reactions to concomitant medications, or progression of disease states.

Note: Pregnancy must be documented as an adverse event and must be reported to the clinical monitor and to the Sponsor immediately upon learning of the event.

Serious Adverse Event (SAE) – An SAE is any adverse event that led to any of the following:

- Death
- Serious deterioration in the health of the subject that resulted in any of the following:
- Life-threatening illness or injury
- Permanent or persistent impairment of a body structure or a body function
- Hospitalization or prolongation of patient hospitalization
- Medical or surgical intervention to prevent life-threatening illness or injury or permanent impairment to a body structure or a body function.
- Chronic disease
- Foetal distress, foetal death or a congenital physical or mental impairment of birth defect.

Diagnoses and conditions that are considered Ocular Serious Adverse Events include, but not limited to:

- Microbial Keratitis (MK)
- Iritis (including cells in the anterior chamber)
- Permanent decrease in best spectacle corrected visual acuity equivalent to 2 acuity lines or greater
- Central Corneal Opacity
- Central Corneal Neovascularization
- Uveitis
- Endophthalmitis
- Hypopyon
- Hyphemia
- Penetration of Bowman's Membrane
- Persistent Epithelial Defect
- Limbal cell Damage leading to Conjunctivalization

Significant Adverse Events – are defined as events that are symptomatic and warrant discontinuation (temporary or permanent) of the contact lens wear

Diagnoses and conditions that are considered Ocular Significant Adverse Events include, but not limited to the following:

- Contact Lens Induced Peripheral Ulcer (CLPU)
- Significant Infiltrative Events (SIE)
- Superior Epithelial Arcuate Lesions (SEALs)

Clinical Study Protocol

Johnson & Johnson Vision Care, Inc.

- Any Temporary Loss of > 2 Lines of BSCVA
- Other grade 3 or higher corneal findings, such as abrasions or edema
- Non-contact lens related corneal events - e.g. Epidemic Keratoconjunctivitis (EKC)
- Asymptomatic Corneal Scar
- Any corneal event which necessitates temporary lens discontinuation > 2 weeks

Non-Significant Adverse Events – are defined as those events that are usually asymptomatic and usually do not warrant discontinuation of contact lens wear but may cause a reduction in wear time. However, the Investigator may choose to prescribe treatment as a precautionary measure.

Diagnoses and conditions that are considered Ocular Non-Significant Adverse Events include, but not limited to the following:

- Non-significant Infiltrative Event (NSIE)
- Contact Lens Papillary Conjunctivitis (CLPC)
- Superficial Punctate Keratitis (SPK)
- Conjunctivitis: Bacterial, Viral, Allergic
- Blepharitis
- Meibomianitis
- Contact Dermatitis
- Localized Allergic Reactions
- Any corneal event not explicitly defined as serious or significant adverse event, which necessitates temporary lens discontinuation < 2 weeks

Adverse Device Effect (ADE) – An ADE is an “adverse event related to the use of an investigational medical device.”

NOTE 1: This definition includes adverse events resulting from insufficient or inadequate instructions for use, deployment, implantation, installation, or operation, or any malfunction of the investigational medical device.

NOTE 2: This definition includes any event resulting from use error or from intentional misuse of the investigational medical device.¹

Unanticipated Adverse Device Effect (UADE) – A UADE is any serious adverse effect on health or safety or any life-threatening problem or death caused by, or associated with, the test article, if that effect, problem, or death was not previously identified in nature, severity, or degree of incidence in the investigational plan, Investigator’s Brochure or protocol, or any other unanticipated serious problem associated with the test article that relates to the rights, safety and welfare of subjects.

13.2. Assessing Adverse Events

In conjunction with the medical monitor, the Investigator will evaluate adverse events to ensure the events are categorized correctly. Elements of categorization will include:

- Seriousness/Classifications (see definition in section 13.1).

Clinical Study Protocol

Johnson & Johnson Vision Care, Inc.

- Causality or Relatedness – i.e. the relationship between the test article, study treatment or study procedures and the adverse event (not related, unlikely related, possibly related, or related - see definition in section 13.2.1).
- Adverse Event Severity – Adverse event severity is used to assess the degree of intensity of the adverse event (mild, moderate, or severe - see definition in section 13.2.2).
- Outcome – not recovered or not resolved, recovering or resolving, recovered or resolved with sequelae, recovered or resolved, death related to adverse event, or unknown.
- Actions Taken – none, temporarily discontinued, permanently discontinued, or other.

13.2.1. Causality Assessment

Causality Assessment – A determination of the relationship between an adverse event and the test article. The test article relationship for each adverse event should be determined by the investigator using these explanations:

- Not Related- An adverse event that is not related to the use of the test article, study treatment or study procedures.
- Unlikely Related – An adverse event for which an alternative explanation is more likely, e.g. concomitant treatment, concomitant disease(s), or the relationship of time suggests that a causal relationship is not likely.
- Possibly Related – An adverse event that might be due to the use of the test article, or to the study treatment or study procedures. An alternative explanation, e.g. concomitant treatment, concomitant disease(s), is inconclusive. The relationship in time is reasonable. Therefore, the causal relationship cannot be excluded.
- Related – An adverse event that is listed as a possible adverse effect (device) or adverse reaction (drug) and cannot be reasonably explained by an alternative explanation, e.g. concomitant treatment of concomitant disease(s). The relationship in time is very suggestive, e.g. it is confirmed by de-challenge and re-challenge.

13.2.2. Severity Assessment

Severity Assessment – A qualitative assessment of the degree of intensity of an adverse event as determined by the Investigator or reported to him/her by the subject. The assessment of severity is made irrespective of test article, study treatment or study procedure relationship or seriousness of the event and should be evaluated according to the following scale:

- Mild – Event is noticeable to the subject but is easily tolerated and does not interfere with the subject's daily activities.
- Moderate – Event is bothersome, possible requiring additional therapy, and may interfere with the subject's daily activities.
- Severe – Event is intolerable, necessitates additional therapy or alteration of therapy and interferes with the subject's daily activities.

13.3. Documentation and Follow-Up of Adverse Events

The recording and documenting of adverse events (ocular and non-ocular) begin when the subjects are exposed to the test article, study treatment or study procedure. Adverse events

Clinical Study Protocol **Johnson & Johnson Vision Care, Inc.**

reported before the use of test article, start of study treatment, or study procedures will be recorded as medical history. However, if the condition deteriorates at any time during the study it will be recorded and reported as an AE. Untoward medical events reported after the subject's exit from the study will be recorded as adverse events at the discretion of the Investigator.

Upon finding an adverse event, the Principal Investigator will document the condition in the subject record and in the eCRFs and complete the Adverse Event eCRF.

Complete descriptions of all adverse events must be available in the subject record. All Adverse Events including local and systemic reactions not meeting the criteria for "serious adverse events" shall be captured on the appropriate case report form or electronic data system. All adverse events occurring while the subject is enrolled in the study must be documented appropriately regardless of relationship.

It is the Investigator's responsibility to maintain documentation of each reported adverse event. All adverse events will be followed in accordance with applicable licensing requirements. Such documentation will include the following:

- Adverse event (diagnosis not symptom).
- Drawings or photographs (where appropriate) that detail the finding (e.g., size, location, and depth, etc.).
- Date the clinical site was notified.
- Date and time of onset.
- Date and time of resolution.
- Adverse event classification, severity, and relationship to test articles, as applicable.
- Treatment regimen instituted (where appropriate), including concomitant medications prescribed, in accordance with applicable licensing requirements.
- Any referral to another health care provider if needed.
- Outcome, ocular damage (if any).
- Likely etiology.
- Best corrected visual acuity at the discovery of the event and upon conclusion of the event, if the AE is related to the visual system.

Upon discovery of an AE that is deemed 'possibly related' or 'related' to the test article or study procedures (whether related to the visual system or not), an AE review form [REDACTED] must be completed. Additional dated and initialed entries should be made at follow-up evaluations. Separate forms must be completed for each eye if the AE is bilateral.

In addition, if an infiltrate(s) is present, he/she will complete the Corneal Infiltrate Assessment eCRF. Where necessary, a culture of the corneal lesion will be collected to determine if the infection is microbial in nature. If cultures are collected, the date of culture collection and laboratory utilized will be recorded.

Changes in the severity of an AE shall be documented to allow an assessment of the duration of the event at each level of intensity to be performed. Adverse events characterized as

Clinical Study Protocol

Johnson & Johnson Vision Care, Inc.

intermittent require documentation of the onset and duration of each episode. Changes in the assessment of relationship to the Test Article shall also be clearly documented.

Subjects who present with an adverse event shall be followed by the Investigator, within licensure, until all signs and symptoms have returned to pre-treatment status, stabilized, or been satisfactorily resolved. If further treatment beyond licensure is required, the patient will be referred to the appropriate health care provider. The Investigator will use his/her clinical judgment as to whether a subject reporting with an adverse event will continue in the study. If a subject is discontinued from the study, it will be the responsibility of the Investigator to record the reason for discontinuation. The Investigator will also document the adverse event appropriately and complete the Adverse Event eCRF. Any subjects with ongoing adverse events related to the test article, study treatment or study procedures, as of the final study visit date, should be followed to resolution of the adverse event or until referral to an appropriate health care provider, as recommended by the Investigator. Non-ocular adverse events that are not related to the test article, study treatment, or study procedures may be recorded as "ongoing" without further follow-up.

13.4. Reporting Adverse Events

The Investigator will notify the Sponsor of an adverse event by e-mail, facsimile, or telephone as soon as possible and no later than 24 hours from discovery for any serious /significant adverse events, and 2 days from discovery for any non-significant adverse event. In addition, a written report will be submitted by the Principal Investigator to the IEC/IRB according to their requirements (section 13.4.2). The report will comment whether the adverse event was considered to be related to the test article, study treatment or study procedures.

13.4.1. Reporting Adverse Events to Sponsor

Serious/Significant Adverse Events

The Investigator will inform the sponsor of all serious/significant adverse events occurring during the study period as soon as possible by e-mail or telephone, but no later than 24 hours following discovery of the event. The Investigator is obligated to pursue and obtain information requested by the Sponsor in addition to that information reported on the eCRF. All subjects experiencing a serious/significant adverse event must be followed up and all outcomes must be reported.

When medically necessary, the Investigator may break the randomization code to determine the identity of the treatment that the subject received. The Sponsor and study monitor should be notified prior to unmasking the test articles.

In the event of a serious/significant adverse event, the Investigator must:

- Notify the Sponsor immediately.
- Obtain and maintain in the subject's records all pertinent medical information and medical judgment for colleagues who assisted in the treatment and follow-up of the subject.

Clinical Study Protocol

Johnson & Johnson Vision Care, Inc.

- Provide the Sponsor with a complete case history which includes a statement as to whether the event was or was not related to the use of the test article.
- Notify the IEC/IRB as required by the IEC/IRB reporting procedure according to national regulations.

Unanticipated (Serious) Adverse Device Effect (UADE)

In the event of an Unanticipated (Serious) Adverse Device Effect (UADE), the Investigator will submit a report of the UADE to the Sponsor and IEC/IRB as soon as possible, but no later than 24 hours after the Investigator first learns of the effect. This report is in addition to the immediate notification mentioned above.

The Sponsor must conduct an evaluation of the UADE and must report the results of the evaluation to FDA, the IEC/IRB and participating Investigators within 10 working days after the Sponsor first receives notification of the effect.

Non-Serious Adverse Events

All non-serious adverse events, including non-serious adverse device effects, will be reported to the sponsor by the Investigator no later than 2 days from discovery.

13.4.2. Reporting Adverse Events to the Responsible IEC/IRB and Health Authorities

Adverse events that meet the IEC/IRB requirements for reporting must be reported within the IEC/IRB's written guidelines. Each clinical site will refer to and follow any guidelines set forth by their Approving IEC/IRB. Each clinical site will refer to and follow any guidelines set forth by their local governing Health Authorities.

The Sponsor will report applicable Adverse Events to the local health authorities according the written guidelines, including reporting timelines.

13.5. Event of Special Interest

None.

13.6. Reporting of Pregnancy

Subjects reporting pregnancy (by self-report) during the study will be discontinued after the event is recorded as an Adverse Event. Once discontinued, pregnant participants and their fetuses will not be monitored for study related purposes. Pregnant participants are not discontinued from contact lens or solution related studies for safety concerns, but due to general concerns relating to pregnancy and contact lens use. Specifically, pregnant women are discontinued due to fluctuations in refractive error and/or visual acuity that occur secondary to systemic hormonal changes, and not due to unforeseen health risks to the mother or fetus.

Clinical Study Protocol

Johnson & Johnson Vision Care, Inc.

14. STATISTICAL METHODS

14.1. General Considerations

Statistical Analysis will be undertaken by the sponsor or under the authority of the sponsor. A general description of the statistical methods to be implemented in this clinical trial is outlined below.

All data summaries and statistical analyses will be performed using the Statistical Analysis System (SAS) software Version 9.4 or higher (SAS Institute, Cary, NC). Throughout the analysis of data, the results for each subject/eye will be used when available for summarization and statistical analysis. Unscheduled visits will be summarized separately and will be excluded from the statistical analysis.

Summary tables (descriptive statistics and/or frequency tables) will be provided for all baseline variables, efficacy variables and safety variables as appropriate. Continuous variables will be summarized with descriptive statistics (n, mean, standard deviation (SD), median, minimum and maximum). Frequency count and percentage of subjects or eyes within each category will be provided for categorical data.

14.2. Sample Size Justification

The plan is to enroll 170 subjects with a target of at least 153 subjects to complete. No historical 2 by 2 crossover study was available to estimate the treatment difference of the primary and secondary endpoints between the Test (AO1DfA) and the Control (AO1D) on the study population. The Visual Performance HLHC logMAR and Contact Lens Preference from [REDACTED] between 1-Day ACUVUE® Moist Astigmatism and 1-Day ACUVUE® Moist were summarized in Table 7. These estimates are used as references to estimate the power for the primary hypothesis in Table 8 and for the third secondary hypothesis (S3) in Table 11. Due to the lack of historical data, several scenarios are enumerated to estimate the power for the first secondary hypothesis (S1) in Table 9 and similarly for second secondary hypothesis (S2) in Table 10. Scenarios with above 80% power is highlighted in blue. The power calculations were conducted with paired t test for the primary, first and second secondary hypotheses; and with Pearson's chi-square test for the third hypothesis using the POWER procedure in SAS 9.4.

Table 7: Historical Data from [REDACTED]

Endpoint	N Subjects	1-Day ACUVUE® Moist for Astigmatism	1-Day ACUVUE® Moist	Intraclass Correlation
Visual Performance (HLHC logMAR)	72	Mean (SD) -0.09 (0.08)	Mean (SD) -0.02 (0.09)	0.399
Contact Lens Preference	72	N (%) 49 (68.1%)	N (%) 17 (23.6%)	-

Clinical Study Protocol
Johnson & Johnson Vision Care, Inc.

Table 8: Power Calculation for the Visual Performance (HLHC logMAR) for the primary hypothesis with Type I error of 0.05.

Mean Difference (Test - Control)	Standard Deviation	Total Sample Size (n/2 per sequence)	Intraclass Correlation		
			0.3	0.4	0.5
-0.025	0.09	153	0.823	0.876	0.927
-0.070	0.09	153	0.999	0.999	0.999

Table 9: Power of the First Secondary Hypothesis of CLUE Vision score for the first secondary hypothesis (S1) with Type I error of 0.05.

Mean Difference (Test - Control)	Standard Deviation	Total Sample Size (n/2 per sequence)	Intraclass Correlation		
			0.4	0.5	0.6
4	18	153	0.703	0.780	0.863
4	20	153	0.612	0.691	0.785
4	22	153	0.532	0.608	0.705
5	18	153	0.876	0.927	0.968
5	20	153	0.801	0.867	0.930
5	22	153	0.722	0.798	0.878

Table 10: Power of the Visual Performance (HLHC logMAR) for the second secondary hypothesis (S2).

Mean Difference (Test - Spectacles)	Type I Error	Standard Deviation	Total Sample Size (n/2 per sequence)	Intraclass Correlation		
				0.3	0.4	0.5
0.015	0.025	0.09	153	0.992	0.998	0.999
0.015	0.05	0.09	153	0.997	0.999	0.999
0.030	0.025	0.09	153	0.703	0.780	0.863
0.030	0.05	0.09	153	0.803	0.862	0.921

Table 11: Power Calculation for the Contact Lens Preference (superiority) for the third secondary hypothesis (S3).

	Type I Error	Total Sample Size	Proportion

Clinical Study Protocol
Johnson & Johnson Vision Care, Inc.

Proportion Difference (Test - Control)	(2-sided)	(n/2 per sequence)	(Prefer the Control)		
			0.3	0.4	0.5
0.24	0.025	153	0.782	0.771	0.797
0.24	0.05	153	0.858	0.849	0.869
0.32	0.025	153	0.965	0.966	0.979
0.32	0.05	153	0.983	0.983	0.990

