	
Secondary Hypotheses:
 
 1. After 1 week of wear, the mean CLUE vision score for binocular correction with AO1DfA lenses will be superior to that for binocular mean sphere correction with AO1D spherical lenses. 2. After 1 week of wear, subjects will have greater overall preference for binocular correction with AO1DfA lenses over AO1D spherical lenses. 3. After 1 week of wear HLHC VA for correction with AO1DfA lenses will be non-inferior to that for correction with subjects' habitual spectacles, using a non-inferiority boundary of -0.05 logMAR.
Study Design	
This will be a 5-visit, randomized, partially single-masked, bilateral wear, dispensing, 2-treatment \times 2-period crossover study with spectacle-wear washout and wash-in periods. Subjects will be randomized into one of two unique sequences to wear each contact lens correction one at a time (sphere followed by toric or toric followed by sphere sphere). For each of the two wear periods, lenses will be worn bilaterally in a daily wear, daily disposable modality for 7(± 2) days. There will be a 7(± 2) day wash-in period prior to the first study lens wear period, and a 7(± 2) day washout period between the first and second wear periods. During the wash-in and washout periods, subjects will only wear their own habitual spectacle correction (i.e., no contact lens wear). Subjective comfort, vision and handling will be assessed at fitting and follow-up visits for each contact lens wear period using the CLUE questionnaire, and CLUE vision will also be assessed at the end of the washout period. HLHC VA and HLLC VA will be assessed with the study contact lenses at the 1-week follow-up visits and with spectacle wear at the end of the washout period. At the final study visit, contact lens preference will be assessed (i.e., preference between the study contact lenses) as well as overall correction ranking (i.e., corrections ranked by preference considering both study lenses and habitual spectacles).
 
See the flow chart at the end of the synopsis table for the schematic of the study visits and procedures of main observations (Figure 1).

Sample Size	
This study will have an enrollment target of approximately 170 subjects, with a target of at least 153 to complete (assuming a dropout rate of approximately 10%).

Study Duration	
Total study duration including the enrollment period is anticipated to be approximately 11 weeks.

Clinical Study Protocol

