2.2. Endpoints

Primary endpoint

The primary endpoint will be the HLHC VA for the contact lens wear periods.

HLHC VA will be assessed using ETDRS charts under controlled lighting conditions, which will be monitored and verified each testing day (room illumination greater than 400 lux, and chart luminance between 120 and 200 cd/m²). VA will be scored letter-by-letter in logMAR units.

Secondary Endpoints

Secondary endpoints for this study will be the subject overall preference between sphere (AO1D) and toric (AO1DfA) correction at the final study visit, the CLUE vision score at 1-week follow-up for each contact lens correction (AO1D, AO1DfA) at follow-up, and the HLHC VA with spectacle correction.

Subjective quality of vision will be assessed using Contact Lens User Experience (CLUE) questionnaire. CLUE is a patient-reported outcomes questionnaire to assess patient-experience attributes of soft, disposable contact lenses (comfort, vision, handling, and packaging) in a contact-lens wearing population in the US, ages 18-65. Derived CLUE scores using Item Response Theory (IRT) follow a normal distribution with a population average score of 60 (SD 20), where higher scores indicate a more favorable/positive response.⁸ A 5-point increase in an average CLUE score translates into 10% shift in the distribution of scores for population of soft disposable contact lens wearers.

Clinical Study Protocol

Johnson & Johnson Vision Care, Inc.

Overall preference between AO1D and AO1DfA correction will be assessed using a preference questionnaire at the final visit. The questionnaire will include 'no overall preference' option.

Other Exploratory Endpoints

Exploratory endpoints for this study will be:

Other observations (efficacy):

- High-Luminance, Low-Contrast (HLLC) VA at follow-up, and with spectacle wear at the end of the washout period
- Number of diagnostic lenses required to achieve fit success for the contact lens corrections
- Length of time required to fit the contact lens corrections
- CLUE comfort and handling scores at 1-week follow-up for the contact lens corrections, and CLUE vision with spectacle wear at the end of the washout period
- MRD and NEI-RQL questionnaire response for the contact lens corrections and with spectacle wear at the end of the washout period
- Subjective ranking of corrections (sphere, toric, and habitual spectacles) in order of preference at the final visit

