5.1	Wear time and compliance	Record the subjects wearing time and comfortable wearing time. Subjects must have worn lenses for at least 8 hours on at least 5 days during the dispensing period, and for at least 1 hour prior to attending this visit. Collect any unworn study lenses from the subject.
5.2	Review medical history and concomitant medications	Record any changes to the subject's medical history (including adverse events) or concomitant medications.
5.3	Subject reported ocular symptoms	Record any subject reported ocular symptoms in response to a verbal open-ended symptoms questionnaire.
5.4	Contact lens preference and correction ranking questionnaire	Subjects will complete a questionnaire regarding their preference between the two contact lenses worn in this study (first contact lenses worn vs second contact lenses worn, or no preference). Subjects will also be asked to rank all three corrections worn in this study (first contact lenses worn, second contact lenses worn, and own spectacle correction) in order of preference.
5.5	Follow-up PRO questionnaire	Subjects will complete CLUE and MRD questionnaires to assess their experience with the study lenses over the preceding wear period.
5.6	Follow-up NEI-RQL questionnaire	Ask subjects to complete the Follow-up NEI-RQL questionnaire regarding their experience with the study lenses over the preceding wear period.
5.7	Entrance visual acuity	Record the entrance Snellen VA for each eye while wearing the study lenses.

Clinical Study Protocol
Johnson & Johnson Vision Care, Inc.

Visit 5: Follow-up #2																							
Step	Procedure	Details																					

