where Δ is the mean difference in logMAR between Test lens and Control lens (Test minus Control). Non-inferiority will be declared on Per-protocol population if the upper bound of the (1- α) two-sided confidence interval of the mean difference between Test and Control is less than 0.05. The α is the Type I error derived from Gatekeeping strategy and α -propagation in Section 14.4. If the non-inferiority is established, superiority will be declared

Clinical Study Protocol

Johnson & Johnson Vision Care, Inc.

if the upper bound of the confidence interval of the mean difference between Test and Control is less than 0.0.

Contact Lens Preference – (S3)

Contact lens preference question will be analyzed using a baseline-category logistic model, where the response of the Control lens preference is the baseline category. This model will include the experimental design factors: sequence of lens wear, lens wearing period, lens type and the interaction between lens type and lens wearing period as fixed effects. Baseline characteristics known of importance such as age and gender will be included as fixed covariates.

The null and alternative hypotheses for superiority of Test (AO1DfA) lens relative to Control (AO1D) are as follows:

$$H_0: \Delta \leq 1.0$$
$$H_A: \Delta > 1.0$$

where Δ is the odds of the preference for the Test to the preference for the Control (Test divided by Control). Superiority for the Test to the Control lens will be established on ITT population if the lower bound of the $(1 - \alpha)$ % two-sided confidence interval (CI) for least squares mean (LSM) odds (Test divided by Control) of the contact lens preference is greater than 1.0. The α is the Type I error derived from Gatekeeping strategy and α -propagation in Section 14.4.

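### Table 11 powers the preference hypothesis (S3) as two independent groups of 76, but each subject gives one three-way answer: 8 of 12 entries are infeasible and the feasible 0.24 entries are too low

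*Combined protocol and SAP*

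**What the plan says.** S3 is the third secondary hypothesis in section 2.3: greater overall preference for AO1DfA (Test) than for AO1D (Control).

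- **Endpoint.** Section 2.2 states: "The questionnaire will include 'no overall preference' option". At Visit 5 (section 7.2, step 5.4) each subject answers once: "first contact lenses worn vs second contact lenses worn, or no preference".
- **Analysis.** Section 14.6 fits a baseline-category logistic model with Control preference as the reference category. The parameter tested against 1 "is the odds of the preference for the Test to the preference for the Control (Test divided by Control").
- **Sample size.** Section 14.2: "The plan is to enroll 170 subjects with a target of at least 153 subjects to complete". The power for S3 comes from a Pearson "chi-square test for the third hypothesis using the POWER procedure in SAS 9.4".
- **Table 11.** Power at N = 153 is laid out by Test minus Control difference (0.24, 0.32), two-sided alpha (0.025, 0.05) and the proportion preferring the Control (0.3, 0.4, 0.5).
- **Reference data.** Section 14.2 names the Table 7 estimates as the reference for Table 11. Of 72 subjects, 49 (68.1%) preferred the Test-type lens and 17 (23.6%) the Control-type lens.

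**The concern.** A two-group chi-square treats the Test and Control preference proportions as if they came from different people. Here both come from the same 153 answers, which has two consequences.

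First, the Test, Control and no-preference shares must sum to 1, so any scenario with Test plus Control above 1 is impossible. Second, the variance of the difference in shares is that of a single multinomial sample, not of two independent binomials with half the subjects each.

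S3 is a formal hypothesis that receives alpha under the gatekeeping scheme in section 14.4. Table 11 is the only power support given for it, so a reader should be able to rely on its entries.

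**Working it through.** **Inputs.** N = 153, the differences, Control proportions, alphas and stated powers are from section 14.2 and Table 11. The historical split is from Table 7. The response structure is from sections 2.2, 7.2 and 14.6.

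**1. Reproduce Table 11.** Two independent groups of n each, pooled null variance, with c the Control share, t = c + d and p = (c + t)/2:

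Power = Φ{ [d√n − z√(2p(1−p))] / √(c(1−c) + t(1−t)) }, with z the 1 − alpha/2 normal quantile.

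First entry, n = 76 (153/2 rounded down), c = 0.30, t = 0.54, p = 0.42, z = 2.2414:
[0.24 × √76 − 2.2414 × 0.6980] / 0.6771 = (2.0923 − 1.5645)/0.6771 = 0.780, and Φ(0.780) = 0.782.

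| d | alpha | Computed (c = 0.3 / 0.4 / 0.5) | Stated |
|---|---|---|---|
| 0.24 | 0.025 | 0.7822 / 0.7708 / 0.7974 | 0.782 / 0.771 / 0.797 |
| 0.24 | 0.05 | 0.8576 / 0.8489 / 0.8693 | 0.858 / 0.849 / 0.869 |
| 0.32 | 0.025 | 0.9650 / 0.9664 / 0.9795 | 0.965 / 0.966 / 0.979 |
| 0.32 | 0.05 | 0.9826 / 0.9833 / 0.9904 | 0.983 / 0.983 / 0.990 |

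All 12 agree to within 0.001. Other group sizes do not fit: for the first entry, 76.5 per group gives 0.785, 77 gives 0.788 and 153 gives 0.981.

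**2. Check feasibility.** Test + Control = 2c + d:

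| d | c = 0.3 | c = 0.4 | c = 0.5 |
|---|---|---|---|
| 0.24 | 0.84 | 1.04 | 1.24 |
| 0.32 | 0.92 | 1.12 | 1.32 |

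Two columns by four rows, or 8 of 12 entries, exceed 1.

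**3. Power with one answer per subject, n = 153, no covariates.** With s = t + c and d = t − c, the McNemar-type approximation is

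Power = Φ{ [d − z√(s/n)] / √((s − d²)/n) }.

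For 0.54 against 0.30 at alpha 0.025: [0.24 − 2.2414 × 0.07410] / 0.07151 = 1.034, and Φ(1.034) = 0.849.

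The delta-method version on the log odds is Φ{ ln(t/c)/√((1/t + 1/c)/n) − z } = Φ(0.5878/0.1841 − 2.2414) = Φ(0.951) = 0.829.

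Three tests were also evaluated by exact summation over the multinomial distribution:

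| Test / Control | alpha | Stated | Wald log-odds | Score | Exact sign | McNemar-type | Delta |
|---|---|---|---|---|---|---|---|
| 0.54 / 0.30 | 0.025 | 0.782 | 0.846 | 0.850 | 0.830 | 0.849 | 0.829 |
| 0.54 / 0.30 | 0.05 | 0.858 | 0.906 | 0.906 | 0.891 | 0.907 | 0.891 |
| 0.62 / 0.30 | 0.025 | 0.965 | 0.976 | 0.977 | 0.971 | 0.977 | 0.964 |
| 0.62 / 0.30 | 0.05 | 0.983 | 0.988 | 0.988 | 0.986 | 0.989 | 0.981 |

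**4. When nobody is undecided.** At 0.62 against 0.38 the McNemar-type power is 0.773 (alpha 0.025) and 0.851 (alpha 0.05). At 0.66 against 0.34 it is 0.965 and 0.983. These lie within 0.002 of the lowest entry in each row of Table 11 (0.771, 0.849, 0.965, 0.983), so on the normal approximation the two approaches agree there.

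**5. The Table 7 reference.** The historical difference is (49 − 17)/72 = 0.444 and the Control share 0.236. Both lie outside the Table 11 grid. One-sample power at that split is at least 0.9994 by every method at both alphas.

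**The case against.** **Low impact.** No decision turns on these figures. Study success rests on the primary hypothesis, S3 is gated behind the primary hypothesis and S1, and nothing says that S3 set N. Power at the historical split is close to 1. The 80% mark in section 14.2 is only a highlighting rule, and the 0.025 entry governs only if S2 is not rejected. All of this stands and limits the consequence.

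**The gap depends on the undecided share.** The 0.54 against 0.30 scenario implies 16% with no preference, whereas Table 7 leaves 6/72 = 8.3%. At 8.3% and a difference of 0.24 (0.578 against 0.338), one-sample power at alpha 0.025 is 0.791 to 0.815, against 0.773 by the two-group formula, and two of the five methods stay below 80%. At alpha 0.05 it is 0.863 to 0.881 against 0.851. With nobody undecided, some methods fall below the table's row minima (for example 0.757 to 0.767 against 0.771). This stands: the understatement is a statement about the table's own feasible 0.24 scenario, not a general rule.

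**A between-sequence reading.** Table 11 labels N as n/2 per sequence. Comparing Test preference in one sequence with Control preference in the other would involve two independent groups, whose shares could sum above 1. No section describes such a test, it is not the section 14.6 model, the same label heads Tables 8 to 10, and sums above 1 would need a period effect that the plan does not state. This does not rescue the table.

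**The replacement is also an approximation.** The planned model has sequence, period, lens-type and covariate terms that the recalculation omits. True, but it respects the one-answer structure, and Table 11 does not.

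**Table 7 as reference.** Using smaller differences than the historical one is cautious, and a reference need not be a grid point. Adding that scenario is therefore a minor improvement.

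**Conclusion.** The concern holds. Table 11 is arithmetically correct for a comparison the trial does not make. Eight of its 12 entries correspond to preference shares that cannot occur with one answer per subject. The two feasible entries at a difference of 0.24 understate power by about 5 to 7 points at alpha 0.025 (0.782 against 0.829 to 0.850) and 3 to 5 points at alpha 0.05 (0.858 against 0.891 to 0.907). At alpha 0.025 this moves the entry from below to above the plan's 80% mark under all five methods. The feasible 0.32 entries change by little or nothing.

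Two assumptions lie behind this. The 76-per-group structure is inferred from the match on all 12 entries, because the text gives only the test and N. The one-sample powers ignore covariates and assume 153 analysable answers. The finding does not show that S3 is underpowered.

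**What to change.** Recompute Table 11 for a single multinomial sample of 153, using a log-odds or sign-type test of Test against Control preference. State the Test, Control and no-preference shares for each scenario, keep only those with Test plus Control at or below 1, and preferably add one near the Table 7 shares (68.1% and 23.6%). Replace the Pearson chi-square statement in section 14.2 with the method used.

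The cost is one table and one sentence. N, alpha allocation and the S3 analysis in section 14.6 do not change.
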